5.1.4 Visit 4 (Postoperative Day 7, ±2 days)

At Visit 4, the following assessments will be performed:

NOTE: All ocular assessments and VA will be performed bilaterally.

- AEs and changes in concomitant medications
- the unmasked designee must weigh both bottles of study drug
- ocular symptoms
- pediatric VA
- biomicroscopy
- IOP measurement

NOTE: Measurement of IOP must occur after the assessment of ocular symptoms, VA and biomicroscopy

- review study drug administration diary for compliance. Instruct subject's parent/legal guardian to record time of each instillation in the diary and to bring the diary and study drug (both bottles) to their next visit. Remind subject's parent/legal guardian that no other information should be recorded in the diary
- dispense new diary
- the unmasked designee must redispense study drug
- remind subject's parent/legal guardian that the dosing is QID for another week and then BID for one week

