5.1.5 Visit 5 (Postoperative Day 14, ±3 days)

At Visit 5, the following assessments will be performed:

NOTE: All ocular assessments and VA will be performed bilaterally.

- AEs and changes in concomitant medications
- the unmasked designee must weigh both bottles of study drug
- ocular symptoms
- pediatric VA
- biomicroscopy
- IOP measurement

NOTE: Measurement of IOP must occur after the assessment of ocular symptoms, VA and biomicroscopy

- fundoscopy (it is at the Investigator's discretion whether to perform fundoscopy with or without mydriasis)
- review study drug administration diary for compliance. Instruct subject's parent/legal guardian to record time of each instillation in the diary and to bring the diary and study drug (both bottles) to their next visit. Remind subject's parent/legal guardian that no other information should be recorded in the diary
- dispense diary
- the unmasked designee must re-dispense study drug
- remind subject's parent/legal guardian that the dosing is BID for the rest of the week and QD for the last week

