5.8.1 Selection and Timing of Dose

The subject will receive the first dose of study drug by the unmasked designee at the end of the surgery. Either the unmasked designee or the subject's parent/legal guardian will then administer 1 to 2 drops of study drug to the lower cul-de-sac of the study eye once in the evening on the day of surgery and then QID, at approximately 4 hour intervals, beginning on the morning after surgery. QID dosing will continue until postoperative day 14, including dosing at appropriate time intervals on the day of a visit. Dosing of both test articles was subsequently adjusted as described in Section 5.9.

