5.9 Dose Adjustment/Modifications

Treatment will be tapered from QID to BID during the interval between postoperative days 15 and 21. Treatment will be further tapered to QD from postoperative day 22 until day 28, with the last dose being administered on the day prior to Visit 6 (Postoperative Day 28).

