9.2.2 Treatment Compliance

Study drug compliance will be calculated for each subject by taking into account whether a subject takes all doses of study drug as instructed. Compliance will be based solely on the subject diaries. The study drug compliance rate will be presented overall, at Visit 4, Visit 5 and Visit 6. The study drug compliance rate for Visit 5 will be calculated by dividing the total number of dosing recorded in the diary for the subject for that period by the total number of days times 4 and then multiplying by 100. The first day of dosing will be ignored entirely, since subjects may be compliant with any number of doses.

The overall study drug compliance rate will be calculated by dividing the total number of dosing recorded in the diary for a subject across the entire treatment period by the total number of days times 4 for days \leq 14, times 2 for days between days 15 and 21 and times 1 for days between 22 and 28 and then multiplying by 100. The first day of dosing will be ignored entirely, since subjects may be compliant with any number of doses. The number and percentage of subjects in each of the following compliance rate categories will also be reported: (\leq 50%, 51-60%, 61-70%, 71-80%, 81-120%, and $>$ 120%). Percentages will be calculated out of the number of subjects who returned diaries from that dosing period. The number and percentage of subjects in each compliance rate category will be presented overall, at Visit 4, Visit 5 and Visit 6.

10 Statistical Analyses

All efficacy analyses will use a 2-sided alpha = 0.05 test unless otherwise stated. No adjustments will be made for multiplicity testing.

Analyses will be performed on the ITT and PP analysis set for both the primary efficacy endpoint and secondary efficacy endpoints. The safety analyses will be performed on the SAF.

All continuous efficacy endpoints will be summarized graphically by treatment group displaying the mean and corresponding standard errors at each time point for the primary efficacy endpoint or line graphs of the continuous secondary efficacy endpoints over scheduled time.

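### The SAP's Visit 5 compliance rate counts four doses on every day, although Visit 5 may fall on Days 15-17, when the SAP's own schedule is two per day

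*SAP*

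**What the plan says.** SAP 9.2.2 gives two formulas.

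- **Visit 5 rate:** the number of doses recorded in the diary is divided "for that period by the total number of days times 4 and then multiplying by 100". Nothing limits the period to Day 14, and its first and last day are not defined.
- **Overall rate:** the denominator depends on the day. It uses 4 for days up to 14, then "times 2 for days between days 15 and 21 and times 1 for days between 22 and 28".

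Both formulas ignore the first day of dosing.

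The schedule is tied to the postoperative day, not to the visit. SAP 5.8.1: "QID dosing will continue until postoperative day 14, including dosing at appropriate time intervals on the day of a visit". SAP 5.9: "Treatment will be tapered from QID to BID during the interval between postoperative days 15 and 21". Protocol 5.1.5 sets "Visit 5 (Postoperative Day 14, ±3 days", that is, Days 11 to 17. Protocol 5.1.4 sets "Visit 4 (Postoperative Day 7, ±2 days", that is, Days 5 to 9, and tells the site to "dispense new diary" at that visit. SAP section 6 repeats these windows.

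**The concern.** Three of the seven permitted Visit 5 days (15, 16 and 17) come after the scheduled change to two doses a day. If those days are in the period, the Visit 5 formula expects four doses where the overall formula, one paragraph later, expects two. Protocol 7.6.5 defines compliance as the share of prescribed instillations received, and on those days the Visit 5 formula does not measure that. Following the calendar taper lowers the score, and not following it leaves the score at 100%. The rate then partly reflects the date of the visit.

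Visit 5 is the primary time point, so this is the summary a reader would use to judge adherence up to the primary assessment.

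**Working it through.** The documents state no compliance figure to reproduce, so the check is a direct count.

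**Inputs**
- Scheduled doses per day: 4 up to Day 14, 2 on Days 15-21 (SAP 5.8.1, 5.9).
- Visit 4 on Days 5-9, Visit 5 on Days 11-17 (protocol 5.1.4, 5.1.5).
- Assumption: the SAP does not define the period, so two main readings are shown.

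**Formula.** Score of a child who takes every scheduled dose = 100 × (scheduled doses in the period) / (4 × days in the period).

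**Reading A: Day 1 through the Visit 5 day**
- Visit 5 on Day 14: 56/56 = 100%
- Day 15: (56 + 2)/60 = 58/60 = 96.7%
- Day 16: 60/64 = 93.8%
- Day 17: 62/68 = 91.2%

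**Reading B: day after Visit 4 through the Visit 5 day**

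| Visit 5 on | Visit 4 on Day 5 | Visit 4 on Day 7 | Visit 4 on Day 9 |
|---|---|---|---|
| Day 14 | 100% | 100% | 100% |
| Day 15 | 38/40 = 95.0% | 30/32 = 93.8% | 22/24 = 91.7% |
| Day 16 | 40/44 = 90.9% | 32/36 = 88.9% | 24/28 = 85.7% |
| Day 17 | 42/48 = 87.5% | 34/40 = 85.0% | 26/32 = 81.25% |

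The minimum is (5 × 4 + 3 × 2)/(8 × 4) = 26/32 = 81.25%, at one of the 35 in-window pairs of visit days. In 15 of the 35 pairs the adherent child scores below 100%. These are counts of calendar combinations, not probabilities, because the documents give no distribution of visit dates.

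**Which visit days are counted.** The visit-to-visit minimum is 83.3% if both visit days count, 87.5% if the Visit 4 day counts but the Visit 5 day does not, and 85.7% if neither counts. Where the Visit 5 day is left out, a Day 15 visit is scored correctly and only Days 16 and 17 are affected (10 of 35 pairs).

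**Child who stays on four doses a day.** The Visit 5 formula gives 4n/4n = 100% for any period of n days. For Visit 5 on Day 17, day-specific multipliers would give 68/62 = 109.7% under A. Under B they would give 40/34 = 117.6% with Visit 4 on Day 7, and 32/26 = 123.1% with Visit 4 on Day 9.

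**Effect on the reported bands.** All the adherent scores above lie in the 81-120% band. A change of band needs the extreme pair under B plus something more:
- One unrecorded dose gives 25/32 = 78.1% (71-80% band), against 25/26 = 96.2% with day-specific multipliers.
- A child who did not taper would move from 100% to 123.1% (above 120%).

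Under A neither example crosses a band.

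**Meaning of day.** SAP section 6 numbers study days as date minus Day 0 date plus 1, so postoperative Day 14 becomes study day 15. If that numbering were used in 9.2.2, the last scheduled four-dose day would be counted at two.

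**The case against.** **Only the four-dose phase may be meant.** SAP 9.2.2 refers to dosing periods, and the overall formula breaks at Day 14. If the Visit 5 rate stopped at Day 14, a flat multiplier of 4 would be right. This is a possible intention, but the text contains no such limit.

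**The longer period is at least as well supported.** Ignoring the first day of dosing has a purpose in the Visit 5 formula only if the period starts at the beginning of treatment. The revision history also shows that this SAP section was moved from Visit 4/Day 7 to Visit 5/Day 14, alongside the change of primary time point. The new diary at Visit 4 points the other way. This part of the objection stands: a reader might infer that adherent children generally score about 81%, but that figure needs reading B and the extreme visit pair.

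**Children on four doses on Days 15-16 may be following instructions.** Protocol 5.1.3 tells parents at Visit 3 to keep four daily doses for two weeks, and 5.1.4 tells them at Visit 4 to keep them for one more week. Counted from the visit, the second runs to Day 15 or 16 when Visit 4 is on Day 8 or 9, and the first can reach Day 15. This stands too. A reader might infer that such children failed to taper, but the documents conflict on the point.

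**Little depends on the rate.** Compliance is descriptive, it enters no efficacy model, and the overall rate already uses day-specific multipliers. This also stands.

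**Conclusion.** The inconsistency is real and minor. As written, the Visit 5 formula understates compliance with the calendar taper when Days 15-17 enter the period: 91-97% under reading A, 81-95% under reading B, with the Visit 5 day counted. It cannot distinguish children who tapered on the calendar from those who did not in the right direction, since the latter score 100%.

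No fully adherent child seen within the windows leaves the 81-120% band. A reader might infer that the flaw reaches the non-inferiority result through the per-protocol population, because Visit 5 is the primary time point. The documents do not support this: neither the protocol (7.5) nor the SAP (6.1.2) defines that population by a compliance cut-off, and the primary model in SAP 10.1 does not use compliance.

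The conclusion assumes that the period extends beyond Day 14 when the visit does, and that adherence is judged by the calendar schedule on which the SAP's own overall formula rests.

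**What to change.** In SAP 9.2.2:

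1. Compute the Visit 5 rate with the multipliers already used for the overall rate (4 for days up to 14, 2 for days 15-21, 1 for days 22-28), summed over the days in the child's own period.
2. Define the first and last day of that period, including whether the visit days count. If only days up to Day 14 are meant, say so; the multiplier of 4 is then correct.
3. State that days are postoperative days, so that the plus-one numbering in SAP section 6 does not shift the cut points.

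The section also promises Visit 4 and Visit 6 rates without a formula, and the same edit can supply them.

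Separately, the parent instructions in protocol 5.1.3 and 5.1.4 and the calendar taper must be reconciled before four-times-daily dosing on Days 15-16 is counted as non-adherence. The multipliers should follow the reconciled schedule.

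The SAP change costs a few sentences and a small programming change, with no new data.

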10.1 Primary Efficacy Analysis

The primary efficacy analysis will be based on the ITT population with missing data imputed using the last observation carried forward (LOCF) method and the primary endpoint will be mean grade of ACI at Visit 5 (Postoperative Day 14). The mean grade of ACI at Visit 5 (Postoperative Day 14) will be analyzed using an ANCOVA model with treatment as a classification variable and investigational site as a covariate.

The least squares mean for each treatment group, the difference in the least squares mean between the 2 treatment groups (LE Gel minus Pred Forte), and the 2-sided 95% confidence interval for the difference will be presented. The null hypothesis will be rejected and non-inferiority established if the upper limit of the confidence interval is less than 0.35.

To support the interpretation of the primary analysis, the analyses above will be repeated for the PP population; no imputation will be conducted for missing data or for subjects placed on rescue medication for the PP analysis. Any discrepancy between the ITT and PP analyses will be explained.

10.2 Secondary Efficacy Analysis

All secondary analyses will be based on the ITT and PP.

As a secondary analysis, the analysis of the observed mean grade of ACI will be repeated as above for Visits 4 and 6 (Postoperative Days 7 and 28, respectively).

Additional secondary analyses include:

- The proportion of subjects with ACI of Grade 0, Grade 1, Grade 2, Grade 3, and Grade 4 for each visit (Postoperative Days 7, 14, and 28)
- The proportion of subjects with presence/absence and total area, if present, of synechiae in the study eye for each visit (Postoperative Days 7, 14, and 28)
- The proportion of subjects with presence/absence and total number, if present, of precipitates on the implant and cornea in the study eye at each visit (Postoperative Days 7, 14, and 28)

For each of the above endpoints, treatment groups will be compared using the Pearson Chi-squared test or Fisher's exact test as appropriate. Differences between the

proportions of treatment groups and 95% confidence interval about the differences will be presented.

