3.2.3 Rescue Therapy

Subjects will be assessed at Visits 3 through 6 (Postoperative Days 1, 7, 14, and 28) for rescue. A study eye with greater than anticipated inflammation at Visit 3 or, at the following visits, a worsening or no change of the grade of inflammation compared to the previous visit may be eligible for rescue therapy. In some cases a persistent or worsening inflammation may be due to a lack of compliance. This should be explored and rectified. If the Investigator deems rescue necessary, the choice of rescue therapy and dosing shall be determined by the Investigator. Subjects requiring rescue therapy for inflammation will stop treatment with study medication. The subject should be exited from the study and the reason selected for exit should be “rescue therapy” in the eCRF. This should not be reported as an AE unless determined to be an SAE.

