7.6.7 Missing Data

For the primary efficacy endpoint analyzed using the ITT population, missing data and data from subjects placed on rescue medication will be imputed using the LOCF methodology. For the PP analysis, missing data and data from subjects placed on rescue medication will not be imputed.

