6.2 Handling of Missing Data

For the primary efficacy endpoint analyzed using the ITT population, missing data and data from subjects placed on rescue medication prior to Day 14 will be analyzed using

the last observation carried forward (LOCF). For the PP analysis, missing data and data from subjects placed on rescue medication will not be imputed.

Data from unscheduled/repeated visits will be presented in listings and will be included in safety summaries for considering the worst-case scenario.

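### The ITT mean ACI grade at Days 7 and 28 is most naturally observed-case, so Day 28 omits subjects rescued earlier, and the ITT grade proportions have no denominator or rescue rule

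*SAP*

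**What the plan says.** **Primary analysis.** SAP 10.1 states: "The primary efficacy analysis will be based on the ITT population with missing data imputed using the last observation carried forward (LOCF) method". SAP 6.2 sets the scope of that rule: "For the primary efficacy endpoint analyzed using the ITT population, missing data and data from subjects placed on rescue medication prior to Day 14" are handled by LOCF. Protocol 7.6.7 limits its rule to the same endpoint and population: "missing data and data from subjects placed on rescue medication will be imputed using the LOCF methodology". For the per-protocol set, SAP 6.2 says: "For the PP analysis, missing data and data from subjects placed on rescue medication will not be imputed".

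**Secondary means.** SAP 10.2 bases all secondary analyses on ITT and PP, then says: "As a secondary analysis, the analysis of the observed mean grade of ACI will be repeated as above for Visits 4 and 6". The matching sentence in Protocol 7.6.1 does not contain the word 'observed'. SAP 3 gives the SAP precedence over the protocol on statistical methods.

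**Secondary proportions.** SAP 10.2 lists "The proportion of subjects with ACI of Grade 0, Grade 1, Grade 2, Grade 3, and Grade 4 for each visit", for Days 7, 14 and 28, together with synechiae and precipitates. Arms are compared by chi-squared or Fisher's exact test, with CIs for the differences. No ITT denominator is given, and no ITT rule for missing or rescued subjects.

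**Rescue.** Protocol 3.2.3 provides for rescue at Visit 3 when inflammation exceeds what was expected. At later visits, an eye with "a worsening or no change of the grade of inflammation compared to the previous visit may be eligible for rescue therapy". The decision is the Investigator's. "Subjects requiring rescue therapy for inflammation will stop treatment with study medication. The subject should be exited from the study". Protocol 3.2.4 and SAP 5.7 both list the need for rescue as a mandatory reason for discontinuation.

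**The concern.** A rescued subject leaves the study, so anyone rescued before Visit 6 has no scheduled Day 28 grade. The early-termination examination follows the Visit 8 schedule, and no rule assigns its grade to Visit 6. These grades are missing because of the outcome being measured. An observed-case Day 28 comparison labelled ITT is therefore a comparison of subjects whose inflammation did not lead to rescue.

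The proportions have the same problem at all three visits. If percentages are taken over available grades, rescued subjects disappear and the Grade 0 rate looks better than it would with them counted as not cleared. At Day 14 there is also an inconsistency: the ITT mean keeps rescued subjects by LOCF, while the ITT proportions of the same grade at the same visit may not. Day 7 is affected less, because only rescue before Visit 4 matters there.

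At stake are the reading of the secondary efficacy tables and the stated clearance rate, not the primary non-inferiority decision.

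**Working it through.** **1. Which reading of SAP 10.2?** The phrase 'repeated as above' points to SAP 10.1, which is ITT with LOCF. The word 'observed' points to no imputation. SAP 6.2 and Protocol 7.6.7 both restrict LOCF to the primary endpoint, and the SAP added 'observed' to the protocol's sentence. The natural reading is observed-case, with 'as above' carrying over the model, least squares means and CI.

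**2. The plan's own figures (SAP 5.4).** The inputs are SD 0.47, margin 0.35, true difference 0, 60 per arm and two-sided alpha 0.05.
- SE = 0.47 × √(2/60) = 0.0858. Power = Φ(0.35/0.0858 − 1.96) = 98.3% (98.1% with the noncentral t), against 98% stated.
- 120/(1 − 0.12) = 137, against about 140 stated.
- The 12% covers all dropout including rescue: 0.12 × 140 ≈ 17 subjects. It is a planning allowance for the Day 14 endpoint. The rescue share, its split by arm and the Day 28 figure are not given.

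**3. Shift in the Day 28 mean difference.** In one arm let p be the proportion rescued before Visit 6, m the mean grade of the others, and g the rescued subjects' mean last grade minus m. Other missing data are ignored.
- Observed-case mean = m. Mean with rescued subjects kept = (1 − p)m + p(m + g) = m + pg.
- Shift in LE minus PR (observed-case minus rescued kept) = −(pLE·gLE − pPR·gPR). A negative value favours LE.

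All rates and gaps below are assumptions:

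| Rescue LE / PR | Gap LE / PR | Shift (grades) |
|---|---|---|
| 12% / 12% | 1 / 1 | 0 |
| 15% / 9% | 1 / 1 | −0.06 |
| 18% / 6% | 1 / 1 | −0.12 |
| 6% / 18% | 1 / 1 | +0.12 |
| 24% / 12% | 1 / 1 | −0.12 |
| 12% / 12% | 1.0 / 0.5 | −0.06 |
| 12% / 12% | 0.5 / 1.0 | +0.06 |

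With 70 per arm, 18% and 6% are 12.6 and 4.2 subjects.

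**4. Bound on the gap.** The variance between rescued and other subjects, p(1 − p)g², cannot exceed the arm's total variance, so g ≤ SD/√(p(1 − p)). If the Day 14 SD of 0.47 also held at Day 28 (an assumption), then at p = 18% g ≤ 0.47/√(0.18 × 0.82) = 1.22. With a common gap, the limit at 18% v 6% is 0.12 × 1.22 ≈ 0.15 in size.

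**5. Scale.** The 95% CI half-width with 60 per arm, ignoring the site term, is 1.98 × 0.0858 = 0.17.

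**6. Grade 0 rate.** Assume 80% of non-rescued subjects in each arm reach Grade 0 and rescued subjects count as not Grade 0. The rate is then 0.80 × (1 − p).

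| Rescue LE / PR | Rescued left out | Rescued in denominator | Difference LE − PR (rescued kept) |
|---|---|---|---|
| 12% / 12% | 80.0% / 80.0% | 70.4% / 70.4% | 0 |
| 15% / 9% | 80.0% / 80.0% | 68.0% / 72.8% | −4.8 points |
| 18% / 6% | 80.0% / 80.0% | 65.6% / 75.2% | −9.6 points |

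With equal rescue the difference is unchanged, but each arm's rate is overstated by 9.6 points when rescued subjects are left out.

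**The case against.** The case against has five parts.

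- **Observed-case is all but specified for the means.** This stands. A reader might infer that SAP 10.2 contradicts itself, or that LOCF and observed-case are equally open. The documents do not support that: LOCF is confined to the primary endpoint, and 'observed' has a plain meaning. The revision history, as background only, fits a deliberate choice.
- **Carry-forward is not clearly better.** This also stands. It could carry a Day 1 grade to Day 28 and overstate inflammation. The documents give no ground for making it the main Day 28 analysis.
- **The sizes are hypothetical.** True. No document gives rescue rates by arm, grade gaps, a Day 28 SD or a Grade 0 rate. An unchanged low grade can also prompt rescue, so a one-grade gap is not implied. The common-gap limit at 18% v 6% (0.15) is below the CI half-width (0.17).
- **Rescue is reported elsewhere.** It is a discontinuation reason in SAP 7, and SAP 9.1 provides for rescue medication to be listed and, if appropriate, summarized. An imbalance would be visible, but the Day 28 estimates would not reflect it.
- **These endpoints are secondary.** This limits the weight of the point but does not answer it. The proportions still lack an ITT denominator, and the omission is still related to outcome.

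**Conclusion.** The point holds as a worthwhile, inexpensive improvement. Read naturally, the plan gives a Day 28 ITT mean comparison that excludes subjects rescued before Visit 6. It gives ITT proportions at Days 7, 14 and 28, and synechiae and precipitate summaries, with no stated denominator or rescue rule. The Day 14 proportions could therefore rest on different subjects from the Day 14 LOCF mean.

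The firmest consequence is for the level of the Grade 0 rate, which available-case percentages overstate even when rescue is balanced, provided rescued subjects are regarded as not cleared. The consequence for the treatment difference is conditional: zero with equal rates and gaps, and about 0.12 grade in size at an assumed 18% v 6% with a one-grade gap.

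A reader might infer that the plan favours the test drug or endangers the non-inferiority claim. Neither follows. The direction depends on unknown rescue rates and gaps and can go either way, and the Visit 5 ITT analysis has its own explicit rule.

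**What to change.** 1. **Grade proportions (SAP 10.2).** At Days 7, 14 and 28 use all ITT subjects as the denominator. Show 'rescued before visit' and 'missing for other reasons' as categories separate from Grades 0 to 4. Make the between-arm test and CI on Grade 0 versus not Grade 0, with subjects rescued before the visit counted as not Grade 0. A subject rescued at a visit keeps the grade recorded there before rescue. State the ITT denominator for synechiae and precipitates as well.
2. **Means at Visits 4 and 6 (SAP 10.2).** State that 'observed' means observed-case. Beside it, add an ITT analysis that carries forward the last post-operative, pre-rescue grade under the same LOCF rule as the primary analysis.
3. **Unscheduled and early-termination grades (SAP 6.2).** SAP 6.2 now sends unscheduled and repeated-visit data to listings and safety summaries. If such grades, or early-termination grades, are to be used, amend SAP 6.2 so that one rule covers the primary and secondary analyses.
4. **Record the choice in SAP 6.3.** SAP 11 says the interim analysis contains all the final tables, so the rule should be settled before either set is produced.

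**Cost.** A few sentences and minor programming, with no new data for items 1 and 2. The reported Grade 0 level will be less favourable. Carry-forward may overstate inflammation when an early grade, such as Day 1, is carried to Day 7 or Day 28, which is why both analyses of the mean should be shown.

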Posterior Synechiae: Assess for presence of adhesions between the iris and the lens.

0 = Absent

1 = Present*

*If present, indicate the total area of synechiae in full clock hours.

Precipitates: Assess for presence of precipitates on implant and cornea.

0 = Absent

1 = Present*

*If present, indicate the total number of the precipitates.

Hypopyon: Assess presence or absence of hypopyon.

0= Absent

1= Present

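### Synechiae area and number of precipitates are assigned chi-squared/Fisher tests, which ignore order and cannot express a difference in extent

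*SAP*

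**What the plan says.** SAP 10.2 lists three additional secondary analyses at Days 7, 14 and 28.

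- ACI grade: "The proportion of subjects with ACI of Grade 0, Grade 1, Grade 2, Grade 3, and Grade 4 for each visit".
- Synechiae: "The proportion of subjects with presence/absence and total area, if present, of synechiae in the study eye for each visit".
- Precipitates on implant and cornea, in the same form, with total number in place of total area.

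One sentence then sets the method for all three: "For each of the above endpoints, treatment groups will be compared using the Pearson Chi-squared test", with Fisher's exact test as the alternative. The effect measure is the difference in proportions with a 95% CI. Protocol 7.6.1 reads the same way.

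Protocol Appendix B (Biomicroscopy) fixes the scales. For synechiae: "If present, indicate the total area of synechiae in full clock hours". For precipitates: "If present, indicate the total number of the precipitates". Both quantities are named as secondary endpoints in protocol 7.1.2 and SAP 5.2.2.

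ACI grade has a second analysis. The primary ANCOVA in SAP 10.1 models mean grade at Visit 5, and under SAP 10.2 "the analysis of the observed mean grade of ACI will be repeated as above for Visits 4 and 6".

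**The concern.** Clock hours are ordered and the number of precipitates is a count. A chi-squared or Fisher test treats their values as unordered labels, so a consistent shift towards more extensive synechiae counts no more than random scatter across categories. Cut-points are needed and the SAP gives none; if each observed value is its own category, most cells hold very few eyes. The stated effect measure says how many eyes are affected, not how badly.

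These outcomes support a non-inferiority claim. If the test drug led to more extensive synechiae or more precipitates, an insensitive test could let that pass as no evidence of a difference. For ACI grade this is much less of an issue, because the mean-grade model uses the order.

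**Working it through.** **The plan's own figure.** No power is stated for any secondary endpoint. The only stated power, 98% for the primary test (SAP 5.4: 60 per arm, SD 0.47, margin 0.35, true difference 0, two-sided 0.05), reproduces. SE = 0.47 × √(2/60) = 0.0858; 0.35/0.0858 = 4.08; 4.08 − 1.96 = 2.12; power = Φ(2.12) = 98.3% (98.1% with the noncentral t). So 60 per arm is used below.

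**Cost of extra degrees of freedom.** Take an effect that a 1-df ordered test detects with 80% power and spread the same noncentrality over k df:

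| df | 1 | 2 | 3 | 4 | 11 |
|---|---|---|---|---|---|
| Power | 80% | 71% | 64% | 60% | 41% |

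Five grades give 4 df; twelve clock-hour values give up to 11.

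**Synechiae area, simulated.** Assumptions, none from the documents: the share of eyes affected in each arm, and hours among affected eyes distributed as 1 + Poisson(mean − 1), limited to 1–12. Pearson chi-squared is taken over the observed hour values and rank-sum is tie-corrected, both two-sided at 0.05, with 10,000 trials per row.

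| Presence, mean hours (arm 1 vs arm 2) | Affected eyes: chi-squared | Affected eyes: rank-sum | All, absent = 0: chi-squared | All, absent = 0: rank-sum | Presence only |
|---|---|---|---|---|---|
| 20%, 2 vs 20%, 2 (no difference) | 3% | 5% | 3% | 5% | 5% |
| 10%, 2 vs 25%, 3 | 9% | 30% | 31% | 66% | 59% |
| 20%, 2 vs 40%, 3 | 20% | 57% | 55% | 79% | 68% |
| 20%, 2 vs 20%, 4 (extent only) | 47% | 89% | 38% | 6% | 5% |

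In the third row the expected affected eyes are 60 × 0.20 = 12 and 60 × 0.40 = 24, so any comparison of extent rests on about 36 eyes.

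The last row matters for the remedy. Scoring absent as 0 almost hides a pure difference in extent, because unaffected eyes dominate the ranks. Neither rank analysis suffices alone.

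**Choice of estimate.** In the third row about 50% of between-arm pairs tie (mostly both absent), 37% favour one arm and 13% the other. The median pairwise difference, which Hodges-Lehmann estimates, is therefore 0 hours despite a real effect. The win probability is 0.37 + 0.50/2 = 0.62.

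**ACI grade, for contrast.** Simulated at 60 per arm with a proportional-odds shift of 2.5 and assumed grade distributions:

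| Assumed spread | Joint chi-squared | Rank-sum | t-test on grade | Grade 0 vs rest |
|---|---|---|---|---|
| SD 0.49, three grades | 57% | 67% | 66% | 67% |
| SD 0.46, five grades | 35% | 53% | 49% | 54% |
| SD 0.66 | 54% | 74% | 71% | 72% |
| SD 1.03 | 57% | 79% | 78% | 59% |

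The t-test on grade, standing in for the planned mean-grade model without site, is within about 5 points of rank-sum throughout.

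**The case against.** **ACI is already covered.** A reader might infer that an excess of inflammation could be missed. The documents do not support that: mean grade is modelled at Visits 4, 5 and 6, with power close to a rank test. The grade-proportion analysis may also be a set of per-grade 2×2 comparisons, which fits the reporting of differences in proportions, rather than one 2×5 test; the SAP does not say which. With three grades and SD near the planned 0.47, even the joint test loses only about 10 points. This objection stands, so the point does not rest on ACI.

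**Occurrence is covered.** Presence/absence is binary and properly tested. SAP 10.4.3.1 also lists posterior synechiae and precipitates among the biomicroscopy findings and tests treatment-emergent incidence. This stands too: what lacks a suitable comparison is extent.

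**The sentence may be meant for proportions only.** Area and number might then be described under the general rules in SAP section 6. But the sentence covers each listed endpoint, and on this milder reading area and number would have no comparison method at all.

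**The sizes rest on assumed inputs, and Fisher's test was not simulated.** True. The percentages are illustrations. Fisher's test on a table of clock hours would also ignore order.

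**Scoring absent as 0 changes the endpoint.** True. It merges occurrence and extent, whereas the plan reports extent when present. The fix has to say so.

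**Conclusion.** The point holds for total synechiae area and total number of precipitates. Both are named secondary endpoints, both are assigned a test that ignores their order, and no other planned comparison addresses extent. Under the assumed 20% versus 40% presence and mean 2 versus 3 hours, chi-squared has about 20% power among affected eyes against 57% for rank-sum; over all subjects with absent = 0, about 55% against 79%. The size moves with prevalence and mean, which the documents do not give, and precipitate number was not simulated separately.

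It does not follow that the plan is insensitive to ACI differences, or that the presence/absence tests are wrong. Nor is the primary non-inferiority conclusion at risk: these endpoints are secondary, have no power target or multiplicity control, and do not enter the primary decision rule.

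**What to change.** Amend SAP 10.2 before database lock.

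1. Keep chi-squared/Fisher with a risk-difference CI for presence/absence of synechiae and precipitates and for ACI grade proportions. State whether grades are tested separately or jointly.
2. For area and number, replace chi-squared/Fisher with a Wilcoxon rank-sum test over all subjects in the analysis population, absent scored 0, and state that this combines occurrence and extent. Report a win probability with 95% CI, since a Hodges-Lehmann estimate will often be 0 when most eyes are unaffected.
3. Add a comparison of area and number among affected eyes (rank-sum, Hodges-Lehmann estimate, 95% CI). Label it descriptive, because that subset is defined after randomization.
4. A rank or row-mean-score test for ACI grade is optional; it would largely repeat the mean-grade analysis.

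The cost is SAP wording and minor programming on data already collected, plus one more type of effect estimate to present.
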